3.2 Primary Study Endpoints

Primary Efficacy End Point: The primary end point is a mean reduction in corneal staining score after 8 weeks of treatment, as measured by Fluorescein and Lissamine dye staining.

Primary Tolerability End Point: The change in the test substance tolerance between Day 1 (post-dose) and at weeks 2, 4, 6 and 8.

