	8.5.		
	8.6	ADVERSE EVENT REPORTING	
	8.6.		
	8.6.		
	8.6.	-	
	0.0.	8.6.3.1 FOLLOW-UP INFORMATION	
	8.7	STUDY CLOSE-OUT	
	8.7		
	0.7	8.7.1.1 7 CALENDER DAY TELEPHONE OR FAX REPORT.	
		8.7.1.2 15 CALENDER DAY WRITTEN REPORT	
	8.8	FAX NUMBER FOR IND SAFETY REPORTS.	
	8.9	IN CASE OF EMERGENCY	
	8.10	DATA SAFETY MANAGEMENT PLAN	
	8.11	STUDY OVERSIGHT	_
	8.12	REPORTING CHANGES IN STUDY STATUS	
9	DAT	A QUALITY AND SAFETY REVIEW PLAN AND MONITORING	39
	9.1	DATA QUALITY AND MANAGEMENT	39
	9.1	-	
	9.1		
	9.2	SUBJECT ACCRUAL AND COMPLIANCE	
	9.2		

	9.2	2.2 MEASUREMENT AND REPORTING OF PARTICIPANT ADHERENCE TO TREATMENT PROTOCOL	40
g	9.3	STOPPING RULE	40
	9.4	DATA AND SAFETY MONITORING BOARD (DSMB)	40
	9.4		
9	. 5	SAFETY REVIEW PLAN	41
10	CON	NFIDENTIALITY	41
11	sou	JRCE DOCUMENTS	42
1	1.1	RECORDS RETENTION	42
12	ETH	ICAL CONSIDERATIONS	42
13	STU	DY FINANCES	
1	3.1	FUNDING SOURCE CONFLICT OF INTEREST	43
1	3.2	CONFLICT OF INTEREST.	43
1	3.3	SUBJECT STIPENDS OR PAYMENTS	43
14	REF	ERENCES	44
15	APP	ENDIX I	47

SCHEDULE OF VISITS AND PROCEDURES

	gı	(e)	(es)					
	Screening	Day 1 (Pre-Dose)	Day 1 (Post-Dose)	Week 2	Week 4	Week 6	Week 8	Week 10
Informed consent	Х							
Demographic information	Χ							
Medical history/ Con Meds/ Transplant history	Х							
Ophthalmic/ oGVHD history	Χ							
Vital signs		Х		Χ	Χ	X	Χ	Х
Best Spectacle Corrected Visual Acuity		Х						Х
Ocular Surface Disease Index (OSDI)	X	Х		Χ	Χ	X	Χ	Х
Clinical Global Impression (CGI)				Χ	Χ	Х	Χ	Х
Subject Global Assessment (SGA)				Χ	Χ	Χ	Χ	Х
Visual Analogue Scale (VAS)			Х	Х	Х	Х	Х	
Ophthalmic examination (Slit lamp)	Χ	Х		Χ	Χ	Х	Χ	Х
Schirmer 1 test and Fluorescein and Lissamine Dye staining	Х	Х					Х	
Ocular surface Redness (OR) score		Х		Χ	Χ	Χ	Χ	Х
Tear fluid analysis (PicoGreen, Cellometry)		Х					Χ	
Keratograph Oculus Redness Score		Χ			Χ		Χ	
Non-invasive Keratography Tear Film Break-up Time (NIKBUT)		Х			Χ		Χ	
Tear Meniscus Height (TMH)		Χ			Χ		Χ	
TearLab Osmolarity Test		Х			Χ		Χ	
InflammaDry for MMP-9 Protein		Х			Х		Х	
Pregnancy test (urine)*	Х							
Randomization visit		Х						
First study medication		Х						
Drug dispensation visits			Х	Х	Х	Х		
Instruction on study medication self- administration			Х	Х	Х	Х		

Version: 10.0; 07-26-2018

Physical inspection of nose & oropharynx	Х		Х	Х	Х	Х	Х
Adverse Events/ Concomitant Medications	Х	X++	Х	Х	Х	Х	Х
Conjunctival culture**	Х					Х	

^{*}If applicable ++ AEs only

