The most likely discomforts a subject may experience by using rhDNase I administered as eye drops are eye burning or irritation, red watery eyes, or feeling like there is something in the eye. To see how subjects react to the study medication, their first dose will be given by the investigator in the clinic itself. Afterwards subjects will be asked to rate tolerability of the drug on the Visual Analogue Scale. Also, at each visit, subjects will be asked to complete the Visual Analogue Scale.

An allergic reaction to the drug cannot be predicted beforehand. In event of an allergic reaction, the drug will be stopped immediately, and symptoms will be managed appropriately depending on the severity of the reaction.

No single agent has yet been approved by the FDA for GVHD prevention or therapy.³⁴ Contact lenses, commonly used to treat oGVHD, will be withheld during the 14 day wash-out period and over the entire course of the study. Stopping contact lens wear may increase the subject's risk of worsening oGVHD. All study subjects will be encouraged to contact the research team immediately if they experience worsening of oGVHD.

No psychological, social, legal, or financial risk is expected from participating in the research.

There is always a risk of a loss of confidentiality.

2 Study Objectives

The objective of this study is to establish whether patients with ocular graft-vs.-host disease (oGVHD) are able to tolerate receiving rhDNase I 0.1% eye drops four times a day for eight weeks (primary tolerability objective) and to investigate the preliminary efficacy of rhDNase I 0.1% topical eye drop solution in treating oGVHD (primary efficacy objective).

3 Study Design

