3.3.9 Tolerability End Point: Test Substance Tolerance (Visual Analogue Scale)

Subjects will assess their tolerance to the administration of the test medication (placebo/ study drug), utilizing a Visual Analog Scale (VAS). The VAS is a 100 mm horizontal line with verbal descriptors at either end. The VAS ratings will be completed after administration of the test medication on Day 1 (post-dose), week 2, week 4, week 6 and week 8. Subjects will place a single slash mark across the horizontal line between the end labeled "completely intolerable" (0 mm) and "easily tolerable" (100mm). The VAS rating is as follows:

Please rate the degree of comfort or lack of comfort associated with administering the eye drop by making one slash mark on the line below:

Visual Analogue Scale

On the scale of 0 to 100 seen below, please mark where you would rate your tolerability to administration of the test drug.

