Subjects currently treating oGVHD with corticosteroids and/or Restasis will continue these treatments during the whole study. If patients are wearing contact lenses (Soft bandage contact lenses or PROSE lens), they will be asked to discontinue contact lens wear for 1 month prior to being enrolled (Baseline visit) and will be required to not wear contact lenses for the duration of the study (until week 10 visit). The study doctor will provide advice about decreasing oGVHD symptoms with artificial tears, eyelid massage, or warm compresses.

If the subject agrees to enter the study, the first treatment visit will be scheduled. If a washout period is needed, visit 2 will be after 2 weeks (±4 days). If a washout period is not necessary, visit 2 can be scheduled any time in the next 2 weeks after the screening visit.

6.5.2 Visit 2 Day 1 (Randomization and First treatment visit) Prior to first dose (Baseline)

- Vital Signs (blood pressure taken while subject is relaxed in a sitting position for at least 3 minutes, pulse, temperature, and height and weight (at this visit only).
- BSCVA (Snellen's chart)
- OSDI
- Schirmer 1 test and Fluorescein and Lissamine Dye staining
- Keratograph Oculus Redness Score
 - > Non-invasive Keratography Tear Film Break-up Time (NIKBUT)
 - > Tear Meniscus Height (TMH)
- TearLab Osmolarity Test
- InflammaDry Test for MMP-9 Protein
- Baseline Ophthalmic Examination (slit lamp examination, Ocular surface redness score)
- Tear fluid collection for analysis (PicoGreen, Cellometry)
- Physical Inspection of the Nose and Oropharynx
- Conjunctival and eyelid margin cultures
- Record changes in concomitant medication
- Adverse events since screening visit.

Randomization (by pharmacy)

Investigator/designee administers first dose

Post-Dose

RhDNase treatment for ocular GVHD Version: 10.0; 07-26-2018

Page 30 of 47

- Test Substance Tolerance (Visual Analogue Scale; VAS)
- Subjects will be trained on how to self-administer the study eye drops and be given a sufficient supply to last for 2 weeks to take home.
- Subjects will receive a study diary on which to record the day/time of each dose and any adverse effects.
- Post dose evaluation for any adverse effects.

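### The primary tolerability endpoint is change from a rating already taken after the first drop, so discomfort that is constant from that drop cancels out of it

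*Combined protocol and SAP*

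**What the plan says.** The objective in section 2 is to establish whether patients "are able to tolerate receiving rhDNase I 0.1% eye drops four times a day for eight weeks (primary tolerability objective"). Section 3.2 turns this into a change endpoint: "The change in the test substance tolerance between Day 1 (post-dose) and at weeks 2, 4, 6 and 8".

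Section 3.3.9 describes the measure. Subjects mark a 100 mm line running from complete intolerability (0 mm) to easy tolerability (100 mm), rating "the degree of comfort or lack of comfort associated with administering the eye drop". All five ratings follow dosing. The visit schedule and section 6.5.2 list the Day 1 rating under post-dose only, and section 1.5 says of the first dose given in clinic: "Afterwards subjects will be asked to rate tolerability of the drug on the Visual Analogue Scale".

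Section 7.2 compares every outcome between arms over time in a mixed model with treatment, time and their interaction. It does not say whether the VAS response is the raw rating or the change, or which term or visit contrast answers the tolerability question. The documents give no VAS threshold and no sample size or power for this endpoint.

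**The concern.** The objective and the scale anchors both concern level: how tolerable the drops are. The declared endpoint concerns drift from the first post-dose reading. Each rating is by itself a direct reading of tolerability, and subtracting the first one removes whatever was present from the first drop.

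This matters because section 1.5 names burning or irritation among the most likely discomforts, and these can occur at the first instillation. If they persist unchanged, the endpoint does not register them. If they ease without disappearing, the endpoint improves more in the arm that started worse. The primary tolerability result of a Phase I/II trial could then be uninformative or point the wrong way. No formal pass is at stake, because the plan sets no VAS success rule.

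**Working it through.** **The plan's own figure.** Nothing is stated for the VAS. Section 7.1 sizes the trial on corneal staining: difference 3.1 − 1.24 = 1.86, SD 2.5, two-sided alpha 0.05, power 80%. The exact t test gives 29.35, rounded up to 30 per group (power 80.9%), which reproduces the plan. At the 36 enrolled per group, power is 87.6%. Only the 36 carries over to the VAS.

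**Cancellation.** Let the vehicle mean at visit t be μ(t) and the active mean be μ(t) − D at every visit. Change from Day 1 is μ(t) − μ(Day 1) in both arms, so the between-arm difference in change is D − D = 0 for any D. This needs no assumption about SD or correlation.

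**Illustration.** Assumed: equal correlation ρ between visits and a common SD. The leading figures use SD 25 mm and ρ = 0.5; brackets give the range over SD 15–30 mm and ρ 0.3–0.7. Two-sample t test, 70 df, noncentrality Δ / (SD × √(2/36)).

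- SD of single-visit change = SD√(2(1−ρ)) = 25.0 mm
- SD of the five-rating mean = SD√((1+4ρ)/5) = 19.4 mm
- SD of the mean of weeks 2–8 minus Day 1 = SD√((1+3ρ)/4 + 1 − 2ρ) = 19.8 mm

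*Constant deficit.* For 15 mm on the five-rating mean, noncentrality is 15 / (19.36 × 0.2357) = 3.29.

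| Constant deficit | Change rejects | Five-rating level rejects |
|---|---|---|
| 10 mm | 5% | 58% (36–99%) |
| 15 mm | 5% | 90% (67% to about 100%) |
| 20 mm | 5% | 99% (89% to about 100%) |

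*Adaptation: active 25 mm worse on Day 1, 10 mm worse at weeks 2–8.* Change favours active by 25 − 10 = 15 mm. The five-rating mean is worse by (25 + 4×10)/5 = 13 mm.

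- Single-visit change significantly favours active: noncentrality 15 / (25 × 0.2357) = 2.55, giving 71% (42% to about 100%).
- The 4-df treatment-by-time test (4 and 280 df) rejects: 73% (40% to about 100%).
- The mean of weeks 2–8 minus Day 1, a form the protocol does not define, favours active: 89% (61% to about 100%).
- The five-rating level test shows active worse: 80% (55% to about 100%).
- In 57% of 20,000 simulated trials, week 8 change significantly favours active while level is significantly worse.

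*Milder adaptation, single-visit change favouring active.* 20 then 10 mm: 39% (22–95%). 15 then 10 mm: 13% (9–44%).

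*Bounded scale.* Ratings were clipped to 0–100, with a vehicle mean of 70–90 before clipping. A constant 15 mm deficit gives 4.9–5.1% on change and 88–90% on level. In the 25-then-10 mm case, single-visit change favours active in 72–74%.

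*Precision.* The 95% CI half-width of the five-rating mean is 3.4–8.8 mm for one arm and 4.7–12.3 mm for the between-arm difference.

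**The case against.** **The mixed model covers it.** Section 7.2 applies to every outcome, and raw VAS at five visits is a natural response. The treatment term or per-visit contrasts would then show a constant deficit. This is right, and it would be wrong to say that the plan cannot detect one. But the declared endpoint corresponds to the treatment-by-time contrast, and the two readings can point in opposite directions. That choice should not be left until after the data are in.

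**Change is a legitimate measure.** A drop cannot be rated before it is given, and eight weeks was chosen partly to learn about long-term use. Change does describe late deterioration or adaptation, which is a reason to keep it, though not as the primary answer to the stated objective. Section 1.5 also shows that first-dose reactions are meant to be looked at, but it sets no analysis.

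**Other endpoints help.** Eight-week completion (section 3.4) catches intolerance that leads to stopping. Adverse events, diary symptoms and the Day 1 post-dose check may record some discomfort in completers. None of these is a graded reading of persistent discomfort.

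**The deficits are assumed.** This stands. The vehicle differs only in lacking dornase alfa (section 1.2), and the one treated patient in section 1.4 reported no discomfort. The sizes are illustrative; the cancellation does not depend on them.

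**Single-visit change is set against a five-visit mean.** This is a fair point. Level at one visit detects constant deficits of 10, 15 and 20 mm in 39%, 71% and 92%, against 5% for change. In the 25-then-10 mm case, the 80% includes the Day 1 gap; weeks 2–8 alone give 56% and week 8 alone gives 39%. Level is less decisive on these terms, but change still reads zero or the wrong sign.

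**Conclusion.** The concern holds. The endpoint as defined does not match the tolerability objective: a between-arm deficit constant from the first drop has zero expected effect on it, and partial adaptation can make it favour the worse arm. The first statement is exact algebra. The size of the second rests on assumed SD, correlation and deficits: 71% for single-visit change in the 25-then-10 mm case, falling to 13% for 15 then 10 mm. The cancellation is exact only for a constant deficit; one that grows or fades does appear in change. The consequence is for interpretation, and it should be corrected before analysis.

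**What to change.** Define the primary tolerability endpoint as VAS level at Day 1 post-dose and weeks 2, 4, 6 and 8. Model raw VAS in the planned mixed model with Day 1 as an outcome visit. As a covariate, under the working assumptions above, Day 1 would remove a fraction ρ of a constant deficit. Name the term that decides.

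Report the between-arm difference overall and by visit, and each arm's mean level, all with 95% CIs. The arm means are needed because a difference alone misses drops that are equally uncomfortable in both arms. State in advance how the active-arm level will be read; that criterion is for the sponsor to choose, since the protocol gives none. Keep change from Day 1 as a secondary description of adaptation or late deterioration.

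For this endpoint, include all treated subjects with any VAS rating, including the rating requested at withdrawal (section 4.4.2), so that early stoppers are not lost. How sections 7.2 and 7.3 define the analysis population more widely is a separate question.

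The cost is an amendment to the endpoint and analysis wording and minor analysis work. The VAS data, visits and model stay the same.

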3.3 Secondary Study Endpoints

The secondary study endpoints will include:

- 1. The change in the Ocular Surface Disease Index (OSDI) which is a patient's subjective rating scale
- 2. Change in tear secretion as measured by Schirmer I test
- 3. The proportion of eyes achieving complete corneal staining clearance after treatment
- 4. Change in conjunctival surface staining score as measured by Fluorescein and Lissamine dye staining
- 5. The change in subjective ocular surface redness score (OR) using the validated bulbar redness (VBR) grading scale
- 6. Visual acuity change
- 7. Change in frequency of administration of artificial tears or concomitant eye drops
- 8. Change in number of corneal filaments (slit-lamp examination)
- 9. Change in amount of mucoid films (slit-lamp examination)
- 10. Clinical Global Impression (CGI) of change in symptoms from baseline (physician's rating)
- 11. Subject Global Assessment (SGA) of overall change from baseline (subject's rating)
- 12. Change in Non-Invasive Keratograph Tear Break-Up Time (NIKBUT)
- 13. Change in Tear Meniscus Height (TMH)
- 14. Change in Keratograph Ocular Bulbar Redness Score
- 15. Change in MMP-9 Protein Detection
- 16. Change in Tear Fluid Osmolarity
- 17. Change in eDNA abundance in tear fluid
- 18. Change in tear fluid cell count
- 19. Change in eDNA strand length on Schirmer test strip impressions

Corneal filaments are mucous tags that are adherent to the surface of cornea. Mucoid films are mucous collections accumulating on the surface of the eye. The number of such mucus tags/ filaments will be counted on each clinical examination (slit-lamp examination).

3.3.1 Efficacy End Point: Ocular surface Fluorescein and Lissamine Dye staining score

[figure not shown]
Ocular surface staining will be assessed using Fluorescein dye for Cornea and Lissamine Green Dye for conjunctiva. The scoring pattern is represented below.

Fluorescein Dye for Cornea:

Using the insulin syringe, 2 units (20uL) of the 1ml insulin syringe will be drawn out from the fluorescein bottle and fluorescein in the syringe will be released into sterile 1ml Eppendorf vial and capped. Using 5µL fixed pipette and a 10µL pipette tip 5µL of the fluorescein will be drawn from the Eppendorf vial and after slightly pulling down the right lower eye lid of the patient fluorescein will be released into the lower conjunctival sac. After waiting for 30 seconds the process will be repeated in the left eye. Recording of corneal fluorescein staining will be performed by a slit lamp examination after 2 minutes and 30

[figure not shown]
seconds for each eye using the grading system described below. Corneal staining will be graded in 5 zones

Each zone will be graded from 0 to 3 based on the density of punctate staining.

Lissamine Green Dye for Conjunctiva:

Using the insulin syringe, 2 units (20uL) of the 1ml insulin syringe will be drawn out from the Lissamine bottle and Lissamine in the syringe will be released into sterile 1ml Eppendorf vial and capped. Using 5uL fixed pipette and a 10uL pipette tip 5uL of the Lissamine will be drawn from the Eppendorf vial and after slightly pulling down the right lower eye lid of the patient Lissamine will be released into the lower conjunctival sac. After waiting for 30 seconds the process will be repeated in the left eye. Using the slit lamp (white light of moderate intensity) nasal-bulbar and temporal-bulbar conjunctiva will be graded within 2 minutes for each eye.

3.3.2 Efficacy End Point: Ocular Surface Disease Index (OSDI)

The OSDI rating scale has twelve questions in three discrete areas, with responses rated on a five point scale. Subjects will complete this scale on Day 1 prior to first dose (Baseline), week 2, week 4, week 6, week 8 and week 10. The questions and scoring system are shown below:³⁷

HAVE YOU EXPERIENCED ANY OF THE FOLLOWING DURING THE LAST WEEK:

	All of the time	Most of the time	Half of the time	Some of the time	None of the time
Eyes that are sensitive to light?	4	3	2	1	0
Eyes that feel gritty?	4	3	2	1	0
Painful or sore eyes?	4	3	2	1	0
4. Blurred Vision?	4	3	2	1	0
5. Poor vision?	4	3	2	1	0

HAVE PROBLEMS WITH YOUR EYES LIMITED YOU IN PERFORMING ANY OF THE FOLLOWING DURING THE LAST WEEK:

	All of the time	Most of the time	Half of the time	Some of the time	None of the time	
6. Reading?	4	3	2	1	0	N/A
7. Driving at night?	4	3	2	1	0	N/A
8. Working with a computer Or bank machine (ATM)?	4	3	2	1	0	N/A
9. Watching TV?	4	3	2	1	0	N/A

HAVE YOUR EYES FELT UNCOMFORTABLE IN ANY OF THE FOLLOWING SITUATIONS DURING THE LAST WEEK:

	All of the time	Most of the time	Half of the time	Some of the time	None of the time	
10. Windy conditions?	4	3	2	1	0	N/A
11. Places or areas with Low humidity (very dry)?	4	3	2	1	0	N/A
12. Areas that are air conditioned?	4	3	2	1	0	N/A

3.3.3 Efficacy End Point: Clinical Global Impression (CGI)

At each visit, the physician (Principal Investigator) will use his clinical evaluation (all signs and symptoms taken together) to provide a global assessment of the subjects' change in symptoms and signs. The CGI is a follows:³⁸

Question (to physician): In general, compared with the subjects' symptoms and signs at baseline, how would you characterize his/ her overall signs and symptoms now?

The responses will be categorized on a seven point scale as follows:

Marked worsening
Moderate worsening
Minimal worsening
Unchanged
Minimal improvement
Moderate improvement
Marked improvement

3.3.4 Efficacy End Point: Subject Global Assessment (SGA)

At each visit, the subjects will be asked to assess their overall change from baseline. The SGA is as follows:³⁸

Question 1 (to subject): Compared with your first visit, how are your eye symptoms now?

The responses will be categorized on a five point scale as follows:

Much worse Worse About the same Improved Much improved

Question 2 (to subject): Compared with your first visit, how is the mucous strings or mucous discharge from your eyes now?

[figure not shown]
The responses will be categorized on a five point scale as follows:

Much worse Worse About the same Improved Much improved

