Contact lenses, commonly used to treat oGVHD, will be withheld during the course of this study. This is necessary as the proposed primary efficacy outcome measure is corneal Fluorescein and Lissamine Dye Staining. Contact lenses can directly reduce corneal SPK and staining due to ensconcing and acting like a bandage that prevents corneal exposure to tear fluid inflammatory materials. Thus, because of over lapping effects on the primary outcome measure, it may not be possible to attribute any observed clinical benefit to rhDNase I treatment if contact lenses are used concurrently. This approach has been used in other clinical trials that have investigated the use of an anti-inflammatory agent in dry eye disease (NIH funded 'Dry Eye Evaluation and Management (DREAM) study').⁴¹

Stopping contact lens wear may increase the risk of worsening of oGVHD during the wash-out period and during the course of the study. However, because other eye drop treatments will continue during

the wash out period as well as during the course of the study, we do not expect any significant clinical worsening during the study. We do however expect the frequency of use of artificial tears to go up during the wash out period and during the course of the study.

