6.5 Study Assessments

The following detailed procedures are performed at the designated clinic visit. All results will be documented on the subject's medical/research charts, source documents, and CRFs as required. All ophthalmic procedures will be performed on both eyes.

6.5.1 Visit 1 Screening Day -18 to 0

After obtaining informed consent, the following assessments will be performed within fourteen days prior to the subject receiving the first dose of study medication:

- Demographic information including: birth date, gender, race or ethnic origin.
- Medical History including prior medication use and prior procedures: Medical history will be
 obtained by interviewing the subject and will include a history of systemic (acute or chronic)
 GVHD, stem cell transplant history (including the date and type of transplant, degree of
 mismatch, if any, etc.), allergic history (including medications and food), substance abuse history

RhDNase treatment for ocular GVHD Version: 10.0; 07-26-2018

Page 29 of 47

(including alcohol) and a history of medication use (including prescription, OTC, and herbal products) during the past 30 days will also be completed.

- Ophthalmic history including: date when the oGVHD began, verification that the subject has had definite oGVHD, medications used by the subject to treat oGVHD, previous procedures to treat oGVHD. Ocular symptoms due to oGVHD will be quantified using the Ocular Surface Disease Index (OSDI) questionnaire (section 3.3.2).
- Ophthalmic Examination (slit lamp examination, Ocular Surface Redness Score, Fluorescein and Lissamine Dye staining, and a Schirmer 1 test)
- Pregnancy test (urine), if applicable. Women of reproductive age will be asked to use a method
 of birth control that is acceptable to the subject and the study doctor. This may include oral
 contraceptive pills, birth control implants/shots or patches, barrier methods or abstinence.
 Women of reproductive age will not be included in the study if they refuse to use any birth
 control measure, including abstinence.

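### Both Subject Global Assessment questions are anchored to the subject's first visit, not clearly to the Day 1 pre-dose baseline that defines the endpoint

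*Combined protocol and SAP*

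**What the plan says.** Secondary endpoint 11 in section 3.3 is "Subject Global Assessment (SGA) of overall change from baseline". Section 3.3.4 introduces the scale in the same terms: "At each visit, the subjects will be asked to assess their overall change from baseline". Both questions to the subject then use another reference. The first reads "Compared with your first visit, how are your eye symptoms now", and the second, on mucous strings or discharge, opens identically. Each has five ordered responses, collected at weeks 2, 4, 6, 8 and 10.

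Baseline is fixed elsewhere. Section 6.5.2 labels the pre-dose part of Visit 2, Day 1, as baseline, and section 3.3.2 does the same for the OSDI. The visit numbered 1 is a different one: "6.5.1 Visit 1 Screening Day -18 to 0". The physician's global rating in section 3.3.3 asks, "compared with the subjects' symptoms and signs at baseline, how would you characterize his/ her overall signs and symptoms now".

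On what may happen between the two visits, section 5.6 says: "Stopping contact lens wear may increase the risk of worsening of oGVHD during the wash-out period". It also expects artificial-tear use to rise.

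**The concern.** A transition question has meaning only through its reference state. If some subjects think back to screening and others to Day 1, the same response describes different changes, and the data will not show which state each subject used.

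Consider a lens wearer whose symptoms worsen by one category between screening and Day 1, then recover by one category on treatment. Measured from screening, the truthful SGA answer is no change. The physician, rating from baseline, records improvement. At stake are whether the SGA measures its stated endpoint, whether its improved rates can be read as on-treatment change, and whether it can be compared with the CGI.

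**Working it through.** **1. The plan's own figure.** The only design calculation is the sample size for the primary endpoint (section 7.1). The difference is 3.1 − 1.24 = 1.86 with SD 2.5. The normal approximation gives 2 × (1.960 + 0.842)² × 2.5² / 1.86² = 28.4, so 29 per group. The two-sample t calculation gives 29.35, so 30, as stated. This point does not affect that figure.

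**2. Which visit is the first?**

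| Place | Reference |
|---|---|
| 3.3, endpoint 11; 3.3.4 introduction | Baseline |
| 3.3.4, both questions | First visit |
| 3.3.3, CGI | Baseline |
| 6.5.1 | Visit 1 is screening, Day -18 to 0 |
| 6.5.2 | Baseline is Visit 2, Day 1, pre-dose |
| 3.4.2 | Visual acuity at first and last visit; the schedule puts it at Day 1 and week 10, so first visit here means Day 1 |

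The numbering points to screening and section 3.4.2 points to Day 1. The anchor is therefore ambiguous.

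**3. How far apart are the two states?** With a wash-out, section 6.5.1 puts Visit 2 at 2 weeks ± 4 days after screening: 14 − 4 = 10 to 14 + 4 = 18 days. Without one, it falls within 2 weeks. Section 1.5 describes a 14-day wash-out, which fits this interval. Sections 4.2, 5.6 and 6.5.1 ask for lenses to be stopped 1 month before the baseline visit, which does not fit a window of at most 18 days. On that version, lenses would already be off at a screening visit held within the window.

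**4. Effect on the comparison.** Wash-out ends before the first dose, and section 7.2 compares rhDNase with vehicle over time. Section 5.3 ties the allocation list to an ID number given at screening, but subjects and research staff are masked and nobody is treated before Day 1. A change before Day 1 is thus unrelated to arm.

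**5. Illustration.** The documents give neither the share of lens wearers nor the amount of worsening, so every input here is assumed except 36 per arm. A standard normal latent response is cut at ±0.5 and ±1.5 into five categories scored 1 to 5. A share of subjects in both arms is shifted towards worse by 0.5 or 1.0 SD. The true effect is 0 or 0.7 SD. The test is a Wilcoxon test at one visit, with 4,000 simulations per setting. It is a simplification of the planned mixed-effects ordinal model. Selected settings:

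| True effect (SD) | Share shifted | Shift (SD) | Mean SGA, vehicle / rhDNase | Difference | Rejection rate |
|---|---|---|---|---|---|
| 0 | 0% | none | 3.00 / 3.00 | 0.00 | 4.6% |
| 0 | 50% | 1.0 | 2.54 / 2.54 | 0.00 | 4.1% |
| 0 | 100% | 1.0 | 2.07 / 2.07 | 0.00 | 4.9% |
| 0.7 | 0% | none | 3.00 / 3.66 | 0.66 | 77.3% |
| 0.7 | 20% | 1.0 | 2.81 / 3.47 | 0.66 | 72.6% |
| 0.7 | 50% | 1.0 | 2.54 / 3.19 | 0.65 | 69.6% |
| 0.7 | 100% | 0.5 | 2.52 / 3.19 | 0.67 | 78.1% |
| 0.7 | 100% | 1.0 | 2.07 / 2.71 | 0.64 | 77.6% |

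Both means fall together and the difference hardly moves. The largest power loss is 77.3 − 69.6 = 7.7 points, where the sample is split evenly between shifted and unshifted subjects. The simulation error of a power near 77% is √(0.77 × 0.23 / 4,000) = 0.7 points, so the values just above 77.3% are not a gain. The number of shifted subjects is drawn separately in each arm, so chance imbalance is included.

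**The case against.** A reader might infer that worsening in the wash-out is counted against rhDNase. The documents do not support this. The worsening precedes treatment and is expected equally in both arms. In the example above, a matching vehicle subject who does not recover would answer one category worse, so the one-category contrast survives. Nor do they support the flat statement that first visit means screening, given section 3.4.2 and the introduction to section 3.3.4.

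Three further objections carry weight. Section 5.6 says no significant clinical worsening is expected, because other eye drops continue. It also requires existing eye treatments to have been in use for at least 30 days before baseline, which limits drift in subjects without lenses. And on the 1-month version of the lens rule, much of any shift could precede screening. These make a large shift less likely. They do not exclude one: section 5.6 still names the risk, and at screening the study doctor advises on tears, lid massage and compresses (section 6.5.1), which may alter symptoms before Day 1 in any subject.

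It is also true that the SGA is one of 19 secondary endpoints, that the OSDI captures symptoms with an explicit Day 1 baseline, and that SGA and CGI already differ in rater, content and number of categories. That limits the consequence. The unclear anchor still adds an avoidable cause of disagreement.

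Section 3.4.2 does not settle the matter for respondents, because it instructs staff. A subject who consented and was examined at screening may well regard that as the first visit.

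**Conclusion.** The mismatch is real and limited in effect. The endpoint is change from Day 1 pre-dose, while the questions name a visit that is screening by number and Day 1 by one other usage. The consequences are some added noise, absolute response rates in both arms that cannot be read as change from Day 1, and possible disagreement with the CGI unrelated to treatment. The rhDNase-versus-vehicle comparison is not biased. Allocation is not stratified by lens wear, so chance imbalance could tilt a single sample, in either direction.

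The size cannot be derived from the documents. The power loss, from none to about 8 points, rests on the assumed shares, shifts and effect above. The wording is worth correcting because no analysis can recover the anchor a subject had in mind.

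**What to change.** Reword both SGA questions to the Day 1 pre-dose anchor, for example: *Compared with the day you started the study drops (before your first drop), how are your eye symptoms now?* Make the same change to the mucus question. If any responses have already been collected, record which wording each was given under.

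The cost is one phrase in two questions and a small departure from the source wording of the item. No visit, assessment or sample-size change follows.

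Separately, the 14-day lens statement (section 1.5) and the 1-month statements (sections 4.2, 5.6 and 6.5.1) contradict each other against the screening window and must be reconciled.
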